## 2 STUDY OBJECTIVES

### 2.1 OBJECTIVES

#### 2.1.1 Primary Objective

To investigate whether the inflammatory response to infection/sepsis is dependent on the type of intravenous fluid used during resuscitation in the Emergency Department.

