### 2.2 ENDPOINTS

This study is exploratory in nature and we have not set primary or secondary endpoints. However, prospective planning for analysis has been conducted and is detailed in Section 9.2 Proposed Analysis.

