## 6.2 BLOOD SAMPLING

Participants in the MIS-ABC trial will have samples taken at three points:

- Baseline (0 hrs): this sample will be taken at the point of enrolment into the sub-study, with the aim of characterising the inflammatory response to sepsis before, or at, the point of administration of the trial intervention.
- Second sample (12 ±4 hrs) after enrolment
- Last sample (24 ± 6 hrs) after enrolment

In each case, two samples will be taken sequentially, from the same point of access. In order to minimise burden to the participants, the study team will work with the clinical team to identify opportunities to take blood simultaneously with routine sampling, as well as identifying sampling options which use existing points of access. Examples of this include:

- Taking research samples at the same time that venepuncture is being performed for routine clinical samples (e.g. taking the research samples with the routine samples from the same 'butterfly needle')
- Taking research samples at the same time that a new, or re-sited, point of vascular access is inserted (e.g. taking the research samples when a new peripheral cannula is inserted)
- Taking research samples from an existing port of vascular access which allows sampling (e.g. taking research samples from an arterial line, a central line or a PICC).

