# 9 STATISTICS AND DATA ANALYSIS

## 9.1 SAMPLE SIZE CALCULATION

Whilst a sample size of 300 has been calculated for the main ABC Sepsis study, as this sub-study is an exploratory analysis no sample size calculation has been conducted. The majority of existing work on cytokine and RNA response focuses on sampling dates in a different context: over the course of days to weeks in patients presenting to hospital with sepsis. Our work will provide a foundation upon which to build further larger studies. We aim to recruit a minimum of 70, which has been selected because it confers a greater than 90% likelihood of incorporating 30 or more participants in the smaller group, assuming equal likelihood of

randomisation to each arm. 30 is a consensus figure arrived at by expert co-authors of the study with experience in related work in critical care research [25]. We anticipate enrolment would not continue beyond 80 participants: at this sample size there is a 99% likelihood of including at least 30 participants in each arm.

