## 9.2 PROPOSED ANALYSES

This project is primarily an exploratory analysis. We will report results by group as defined by the treatment arm into which they are enrolled, as well as by key outcomes (e.g. mortality at 30 days, admission to ICU). No interim analyses will be conducted.

Analysis will be conducted, across treatment arms, of individual biomarkers as part of our cytokine panel, whether at individual timepoints or in terms of the change, and rate of change, from baseline results. It will also incorporate analysis of grouped variables (e.g. 'pro-inflammatory cytokines' versus 'anti-inflammatory cytokines', or those known to be representative of specific pathophysiological damage like endothelial damage), again at individual timepoints or in terms of the change, and rate of change, from baseline. Further grouping may be taken, depending on the spread of our physiological data, to determine differences between 'responders' to fluid challenge versus 'non-responders' in either treatment arm.

Taken as a whole, we will assess the accuracy of these biomarkers as predictors of our key clinical endpoints, with consideration of sensitivity, specificity and positive or negative predictive values. Receiver operator characteristic analysis will be explored for biomarkers with significant biological plausibility or which show promise in the preceding analysis. Transcriptomic data from RNA-seq will be interrogated to determine changes in RNA abundance at the gene level between sample points and by treatment arm, as well as at the transcript isoform level.

Using the inclusion criteria mentioned before, it is plausible that we will include patients who ultimately are diagnosed with a pathology other than sepsis as a reason for their presentation to hospital. The inclusion of the results of such patients in the described analyses will be decided on discussion with the broader study team in the context of the frequency of this occurrence as well as the potential bias this might incur with the specific analysis.

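### Section 9.2 names no baseline-adjusted between-arm cytokine comparison; adding one is an optional, cheap gain in precision, of a size that the documents do not fix

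*Protocol*

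**What the plan says.** Section 2.1.1 gives the primary objective as a comparison of the two fluids: "To investigate whether the inflammatory response to infection/sepsis is dependent on the type of intravenous fluid used during resuscitation". Section 2.2 sets no primary or secondary endpoint but states that "prospective planning for analysis has been conducted and is detailed in Section 9.2 Proposed Analysis".

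Section 9.2 then lists the between-arm comparisons. Single cytokines are to be compared "whether at individual timepoints or in terms of the change, and rate of change, from baseline results", and groups of cytokines "again at individual timepoints or in terms of the change, and rate of change, from baseline". No section mentions a comparison that uses the baseline value as a covariate, and section 9.2 names no test or model for the arm comparison.

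Section 6.2 plans a baseline sample at enrolment, with the aim of describing the inflammatory response "before, or at, the point of administration of the trial intervention". Follow-up samples are due at 12 (±4) and 24 (±6) hours.

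On numbers, section 9.1 says "We aim to recruit a minimum of 70" and "We anticipate enrolment would not continue beyond 80 participants". It makes no sample size calculation and gives no SD, correlation or precision target.

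**The concern.** If the listed forms are carried out without covariates, each fixes in advance how much of the baseline value is subtracted: none for the value at a timepoint, all of it for the change. Neither is best in general. Which is the more precise depends on how strongly baseline and follow-up correlate and on how their SDs compare. Neither is known beforehand, and both may differ across the 14 cytokines of section 1.1. Estimating the coefficient from the data, as ANCOVA does, is usually at least as precise as the better of the two and removes the need to guess.

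What is at stake is precision for the primary objective in a study of 70 to 80 people. Validity is not at stake, and with no stated precision target none is missed.

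**Working it through.** **Plan's own figure.** There is none to reproduce. The probabilities in section 9.1 concern arm sizes only.

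**Inputs from the protocol.** Total N of 70, with 80 as the expected ceiling (section 9.1). Equal arms of 35 or 40, because section 9.1 works "assuming equal likelihood of" allocation to each arm.

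**Assumed inputs.** Correlation r between baseline and follow-up: 0.3, 0.5, 0.7. Ratio k of follow-up SD to baseline SD: 1 first, then 0.7 to 1.4. The protocol gives no measurement scale; equal SDs would be most plausible on a log scale.

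**Variance of the arm difference**, in units of baseline variance × 2/n, with n per arm:

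- value: k²
- change: k² + 1 − 2rk
- adjusted (ANCOVA): k²(1 − r²) × (N − 3)/(N − 4)

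The last factor is the cost of estimating the slope: 67/66 = 1.0152 at N = 70 and 77/76 = 1.0132 at N = 80.

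**Equal SDs (k = 1), N = 70**

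| r | value | change | adjusted | variance reduction against the better | SE reduction |
|---|---|---|---|---|---|
| 0.3 | 1.00 | 1.40 | 0.91 × 1.0152 = 0.924 | 7.6% | 3.9% |
| 0.5 | 1.00 | 1.00 | 0.75 × 1.0152 = 0.761 | 23.9% | 12.7% |
| 0.7 | 1.00 | 0.60 | 0.51 × 1.0152 = 0.518 | 13.7% | 7.1% |

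At N = 80 the variance reductions are 7.8%, 24.0% and 13.9% (SE 4.0%, 12.8%, 7.2%). A simulation of 40,000 trials with 35 per arm gave 7.6%, 23.6% and 13.9%. Within this range the gain peaks at r = 0.5, where value and change are equally precise.

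**95% CI half-width**, 1.96 × √(2v/n), in SD units, from the better of value and change to adjusted:

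- 35 per arm: 0.47 to 0.45 (r = 0.3), 0.47 to 0.41 (r = 0.5), 0.36 to 0.34 (r = 0.7).
- 40 per arm: 0.44 to 0.42, 0.44 to 0.38, and 0.34 to 0.32. The last is 1.96 × √(2 × 0.5167/40) = 0.315.

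**Unequal SDs, N = 70: variance reduction against the better of value and change**

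| k | r = 0.3 | r = 0.5 | r = 0.7 |
|---|---|---|---|
| 0.7 | 8% | 24% | 48% |
| 0.85 | 8% | 24% | 30% |
| 1.2 | 8% | 12% | 2% |
| 1.4 | 8% | 4% | -1.5% |

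The bottom-right entry is negative because the true slope there is rk = 0.7 × 1.4 = 0.98. Change, which uses a slope of 1, is then almost optimal, and only the cost of estimating the slope remains. For the same reason about 1.5% is lost when r is near 0, where value alone is optimal.

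**Sign disagreement between value and change.** For k = 1 and no true arm difference, the two estimates have correlation √((1 − r)/2). They take opposite signs with probability arccos(√((1 − r)/2))/π = 0.298, 0.333 and 0.373 for r = 0.3, 0.5 and 0.7. With a true difference of 0.5 SD and 35 per arm, simulation gives 4.3%, 3.1% and 2.0%.

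**Not covered.** Rate of change. Its variance also depends on the spread of actual sampling times within the ±4 h and ±6 h windows.

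**The case against.** The strongest objection is that section 9.2 names forms of outcome and not estimators. It specifies no model for the arm comparison, ANCOVA could be used to carry out what it lists, and covariates are commonly left to an analysis plan that may exist but is not shown. This stands to the extent that a reader might infer that the protocol prescribes unadjusted analyses, excludes adjustment or gets something wrong. The text does not support any of those readings. What remains is narrower: section 2.2 presents 9.2 as the place where the analysis is laid out, 9.2 does choose the forms of comparison, and the more efficient one is not among them.

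It is also fair that the size rests on assumed inputs. The 24% is the best case for equal SDs, the gain is 2% or less in some plausible settings, and the study is exploratory. These points limit the claim without removing it.

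A further objection concerns the covariate. A baseline sample before or at the start of fluid is an aim, and section 4.2 admits only people already randomised to the main trial. A sample drawn after the fluid started could be affected by treatment, and adjusting for it could distort the comparison. Change and rate of change share this weakness; the plain timepoint comparison does not. This stands and belongs with the costs.

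Finally, a reader might take the 30 to 37% rate of opposite signs as a main reason to adjust. It applies only when there is no true arm difference, so that both estimates are noise; at a true 0.5 SD difference it is 2 to 4%. Because the unadjusted results would be kept, readers could still see estimates that disagree.

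**Conclusion.** The point holds as an optional improvement in efficiency. Against the better of value and change, adjustment lowers variance by about 8 to 24% and the standard error by 4 to 13%, if r lies between 0.3 and 0.7, the SDs are equal and N is 70 to 80. If the SD ratio may lie anywhere from 0.7 to 1.4, the change in variance runs from a 1.5% loss to a 48% gain. Neither r nor the SD ratio can be taken from the documents. In CI terms the equal-SD gain is mostly a few hundredths of an SD.

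**What to change.** Add to section 9.2 that the lead between-arm comparison of each cytokine and cytokine group at 12 h and 24 h will be adjusted for the baseline value, for example by ANCOVA, which gives the same arm estimate whether the outcome is the value or the change. Keep the unadjusted timepoint, change and rate-of-change results as supporting. Add a sensitivity analysis that uses the recorded sample times (section 7.1) and the start time of the trial fluid (section 7.2) to check the effect of baseline samples drawn after the fluid began.

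The cost is a sentence or two, with no new samples or data. There are three downsides:

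- About 1.5% of variance is lost in unfavourable cases.
- Participants without a baseline value drop out of a simple ANCOVA, as they already do for change and rate of change.
- A late baseline may be affected by treatment, which the sensitivity analysis is there to examine.

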## **1.2 RATIONALE FOR STUDY**

Currently, there is controversy about the optimal fluid choice in patients presenting to hospital with sepsis. Understanding how each fluid type affects the underlying inflammatory process may provide a mechanistic argument for clinician choice, future research and professional recommendations.

MIS-ABC Sepsis is a sub-study of the ABC-Sepsis trial, a pilot feasibility trial recruiting patients with community acquired infection/sepsis with a NEWS2 score of five or more and randomising the participants to receiving either balanced crystalloid or 5% HAS as the intravenous resuscitation fluid up to six hours after randomisation.

MIS-ABC Sepsis will take serial blood samples from a small number of these participants, at hospital presentation and at two further points early during the patient's admission, to allow analysis of how inflammation changes during their course of illness. Investigating temporal change and differences between treatment arms of the main study will allow a nuanced analysis of the interplay between severity of illness, physiological changes over time and any potential differences between fluid treatment arm.

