#### 2.1.2 Secondary Objectives

1. To understand the inflammatory response in patients with community acquired infection/sepsis by the analysis of a panel of cytokines.
2. To evaluate whether the early inflammatory response to infection/sepsis at the time of presentation to secondary care predicts clinically important outcomes.
3. To investigate whether transcriptomic analysis can provide an explanation for varying physiological response to fluid therapy and clinical outcomes in infection/sepsis.

[figure not shown]

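### The optional fluid-responder split in section 9.2 discards about a third or more of the information, has a cut tied to the observed data, and yields non-randomised contrasts; response should be analysed as continuous.

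*Protocol*

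**What the plan says.** Section 2.2 of the Protocol refers the reader to section 9.2 for the analysis planning, so section 9.2 is the stated plan. After the comparisons of cytokines across arms it adds: "Further grouping may be taken, depending on the spread of our physiological data", the purpose being "to determine differences between 'responders' to fluid challenge versus 'non-responders' in either treatment arm". It names no physiological variable, threshold or time window for response.

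Three other places bear on this:

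- **Timing.** Section 1.2 describes the allocated fluid as given "as the intravenous resuscitation fluid up to six hours after randomisation". A response to it is therefore observed after randomisation.
- **Objective.** Secondary objective 3 (section 2.1.2) asks whether transcriptomics "can provide an explanation for varying physiological response to fluid therapy and clinical outcomes in infection/sepsis". It treats response as something that varies, not as present or absent.
- **Status and size.** Section 9.2 states "This project is primarily an exploratory analysis", and section 2.2 states "This study is exploratory in nature and we have not set primary or secondary endpoints". Section 9.1 sets a minimum of 70 participants and says "We anticipate enrolment would not continue beyond 80 participants". That is about 35 to 40 per arm.

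**The concern.** Two features are written into the sentence itself: the grouping has two levels, and it is to follow the data as observed. A third follows from the timing: the groups are formed by something that happens after randomisation and that the allocated fluid may change.

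Each has a consequence. A two-level split of a graded measure loses power, and within one arm a median split leaves only about 17 or 18 participants per group. A cut left open until the data are in can, if cytokine results are in view by then, drift towards the cut that gives a result. Responders and non-responders in an arm may also differ in severity of illness, which can drive both haemodynamic response and cytokine level. A difference between them could then be taken for a biological explanation of fluid response when it is neither randomised nor, perhaps, reproducible in the larger studies that section 9.1 hopes to support.

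**Working it through.** The Protocol gives no error rate, power or threshold for this analysis, so there is no stated figure to reproduce.

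**Inputs.** From section 9.1: 70 to 80 participants and equal chance of either arm, hence 35 per arm at the minimum. Assumed, because the Protocol gives none: two-sided 0.05, normally distributed measures, and correlations between response and log cytokine of 0.3 to 0.5.

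**1. Information kept by a split.** With a fraction p in one group and q the matching normal quantile, relative efficiency is φ(q)² / [p(1 − p)].

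| Split | Calculation | Kept | 70 patients act like |
|---|---|---|---|
| 50/50 | 0.399² / 0.25 | 64% | about 45 |
| 30/70 | 0.348² / 0.21 | 58% | about 40 |
| 20/80 | 0.280² / 0.16 | 49% | about 34 |

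The loss is about 36% at the median and greater elsewhere, however the cut is chosen.

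**2. Power.** Simulated, Pearson correlation against a t test on a median split (3,000 replicates):

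| Assumed correlation | n = 35, continuous | n = 35, split | n = 70, continuous | n = 70, split |
|---|---|---|---|---|
| 0.3 | 41% | 29% | 72% | 52% |
| 0.4 | 70% | 47% | 94% | 79% |
| 0.5 | 90% | 71% | 99% | 95% |

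A separate run at n = 35 gave 67% against 48% at 0.4, and 89% against 70% at 0.5.

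A closed-form check uses power ≈ Φ(atanh(r)·√(n − 3) − 1.96), with n = 35 and √32 = 5.66. A median split multiplies the correlation by √0.637 = 0.798.

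- r = 0.4, continuous: 0.424 × 5.66 − 1.96 = 0.44, giving 67%.
- r = 0.4, split (0.4 × 0.798 = 0.319): 0.331 × 5.66 − 1.96 = −0.09, giving 46%.
- r = 0.5, continuous: 0.549 × 5.66 − 1.96 = 1.15, giving 87%.
- r = 0.5, split (0.5 × 0.798 = 0.399): 0.422 × 5.66 − 1.96 = 0.43, giving 67%.

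The gap is about 20 points at either correlation by every route.

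**3. False positives for one cytokine, with no true association.** Simulated:

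| How the cut is chosen | n = 35 | n = 70 |
|---|---|---|
| Median, set from physiology alone | 4.2% | 5.2% |
| Best of three cuts (tertiles and median) against the cytokine | 10.7% | 11.5% |
| Best of all cuts, 20th to 80th percentile, against the cytokine | 29% | 30% |
| Best of all cuts, 10th to 90th percentile, against the cytokine | 33% | 39% |

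The first row is nominal. Inflation appears only when the cytokine guides the choice.

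**4. Arm-by-response interaction.** Comparing Fisher-transformed correlations between arms of 35 has standard error √(1/32 + 1/32) = 0.25. For 80% power the difference must be (1.96 + 0.84) × 0.25 = 0.70 on that scale. An example is a correlation of 0 in one arm and tanh(0.70) = 0.60 in the other. This is weak at the planned size.

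**The case against.** The best defence is that the analysis is optional and exploratory, in a study with no endpoints and no stated alpha, and that a SAP not shown here may define response. That is fair as far as it goes, and the absence of a definition is not the complaint. But the two-group form and the dependence on observed spread are in the Protocol's own text, and an exploratory label does not give back lost power.

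Three stronger readings are tempting, and the documents do not support them.

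- **A reader might infer that the plan inflates false positives to around 30%.** The sentence ties the grouping to the physiological data, not to cytokine results, and a cut set that way stays near 5%. Inflation needs several cuts tried with cytokine results in view. The Protocol neither states nor excludes this.
- **A reader might infer that arms will be compared within responders, with biased results.** The stated contrast is responders against non-responders in either arm. If arms were compared within responders, simulation with no true fluid effect on the cytokine gives a spurious difference of 0.02 to 0.13 SD. This assumes a fluid effect on response of 0.3 to 0.8 SD and correlations with severity of 0.3 to 0.5. With about 17 responders per arm the standard error is √(2/17) = 0.34 SD, so the bias would be at most about 0.4 of a standard error (0.13 / 0.34). It merits a caution, not a headline.
- **A reader might see responder differences as the study's main route to explaining a fluid effect.** The primary objective concerns fluid type, and section 9.2 describes the RNA analysis by sample point and arm, not by responder status. The link to secondary objective 3 is plausible from its wording but is inferred.

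**Conclusion.** The point holds as an improvement to make in an optional, exploratory analysis. The loss from the two-group form is certain in direction: about 36% of the information at a median cut, and more at uneven cuts. In an arm of 35 that is roughly 20 points of power at correlations of 0.4 to 0.5. These figures assume a roughly linear relation and normal measures, and the correlations are assumptions.

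The false-positive risk is conditional: near 5% if the cut comes from physiology alone, about 11% with three cuts tried against a cytokine, and about 30% or more with all cuts. The weakness is that nothing rules out the latter.

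Whichever cut is used, responder contrasts are non-randomised associations open to confounding by severity, and the Protocol does not say so.

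**What to change.** Replace the sentence on further grouping in section 9.2 with one to this effect: physiological response will be analysed as a continuous measure, adjusted for its baseline value, against log cytokine level within each arm; the measure and its time window will be chosen before cytokine data are linked to clinical data; any arm-by-response interaction is exploratory and has low power at 70 to 80 participants.

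If a responder label is kept for display, fix its definition before linkage, describe its results as non-randomised and hypothesis-generating, and do not interpret arm differences within responders as fluid effects.

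No new data are needed. Section 6.1 already schedules vital signs at baseline and at both later samples. Section 6.4 keeps samples at the sites until recruitment ends, so there is time to fix the measure before cytokine results exist. The costs are that the team must agree the measure and window in advance, and that a continuous result is slightly harder to present than two groups.

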We hypothesise that different types of intravenous fluids used in resuscitation (albumin versus balanced crystalloid) may mediate different pro and anti-inflammatory response as measured by these cytokines. We also hypothesise that plasma levels of these cytokines, measured at time of ED admission, will enable improved differentiation of patients with suspected sepsis who are at high risk of deterioration

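### Section 9.2 lets markers into ROC analysis on observed promise; where promise is judged on outcome in the same 70 to 80 participants, their AUCs are biased upward

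*Protocol*

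**What the plan says.** Section 9.2 sets out the analyses in sequence.

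- Results are reported by treatment arm, "as well as by key outcomes (e.g. mortality at 30 days, admission to ICU").
- Individual and grouped cytokines are compared across arms, at single timepoints and as change or rate of change from baseline.
- Predictive accuracy follows: "Taken as a whole, we will assess the accuracy of these biomarkers as predictors of our key clinical endpoints". The measures named for this step are sensitivity, specificity and the two predictive values.
- Then comes the entry rule for ROC work: "Receiver operator characteristic analysis will be explored for biomarkers with significant biological plausibility or which show promise in the preceding analysis".

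The rule has two routes joined by *or*, so promise is sufficient without plausibility. Promise is given no criterion.

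The ROC work serves the second secondary objective (section 2.1.2), which asks whether "the early inflammatory response to infection/sepsis at the time of presentation to secondary care predicts clinically important outcomes". The matching hypothesis in section 1.1 is that "plasma levels of these cytokines, measured at time of ED admission, will enable improved differentiation of patients with suspected sepsis" at high risk of deterioration. Section 9.1 sets a minimum of 70 participants and expects no more than 80. Section 1.1 lists 14 cytokines.

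**The concern.** If a marker is picked because it separates events from non-events in a sample, its AUC in that sample contains the chance variation that got it picked. The average over picked markers then exceeds the truth, even though each marker's AUC would be unbiased had it been reported regardless.

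The rule permits this. The steps before the ROC sentence include two that use outcome: the split by key outcomes and the accuracy assessment. With few events the chance component is large.

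At stake is how the AUCs will be read. Section 9.1 says "Our work will provide a foundation upon which to build further larger studies", so others are expected to build on the results. A reader needs to tell an AUC for a marker named beforehand from one for a marker picked on its own result. The rule as written does not separate the two.

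**Working it through.** The protocol gives no AUC, event rate or selection threshold, so there is no figure of its own to reproduce. The sizes below are illustrations under stated assumptions.

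**Inputs**

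- N = 70, with 80 as a check (section 9.1).
- 14 markers, counted from the list in section 1.1.
- Events: assumed. Section 1.1 quotes 22% overall sepsis mortality, and 0.22 × 70 = 15.4, taken as 15. This is not a rate for this cohort, and no ICU admission rate is given. Range used: 7 to 21 events (10% to 30%).
- Correlation between markers: assumed 0.3. Markers: normal.
- Promise on outcome: assumed to be either rank-sum p<0.05 against outcome, or being the best of the 14.

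**Step 1: the entry bar, by hand.** With e events and f non-events, the smallest AUC reaching two-sided p<0.05 is about 0.5 + 1.96 × √[(N+1)/(12ef)].

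- 15 of 70: 0.5 + 1.96 × √(71/9,900) = 0.666
- 7 of 70: 0.5 + 1.96 × √(71/5,292) = 0.727
- 21 of 70: 0.5 + 1.96 × √(71/12,348) = 0.649

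With 15 events, a marker whose true AUC is 0.65 cannot enter in the expected direction without showing more than its true value.

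**Step 2: average AUC shown, by simulation** (direction fixed in advance, correlation 0.3).

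| Events / N | True AUC | All 14 reported | Picked at p<0.05 | Best of 14 |
|---|---|---|---|---|
| 7 / 70 | 0.65 | 0.650 | 0.785 | 0.801 |
| 15 / 70 | 0.65 | 0.651 | 0.722 | 0.763 |
| 21 / 70 | 0.65 | 0.650 | 0.705 | 0.750 |
| 18 / 80 | 0.65 | 0.650 | 0.709 | 0.754 |
| 15 / 70 | 0.50 | 0.501 | 0.697 | 0.621 |

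For a true 0.65 and 15 events, the excess is 0.722 − 0.65 = 0.07 under the p<0.05 rule and 0.763 − 0.65 = 0.11 for the single best. In the null row, the p<0.05 column averages only over the data sets where a marker passes in the expected direction; at least one of the 14 does so in 22% of them.

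**Step 3: a mixed panel.** If 4 of 14 markers have true AUC 0.65 and 10 are null (15 of 70), the best marker shows 0.719 while its true AUC averages 0.644, an excess of 0.075.

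**Step 4: direction left free.** If an AUC below 0.5 is turned round, the best of 14 null markers shows 0.663. One null marker fixed in advance already shows 0.568 under the same convention. Selection therefore adds 0.663 − 0.568 = 0.095, about 0.10. Comparing 0.66 with 0.50 would overstate it.

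**Step 5: choice on arm difference only** (70 participants, 15 events, markers independent). Markers with true AUC 0.50, 0.60, 0.65 and 0.70 show 0.500, 0.598, 0.649 and 0.700. This route adds no bias.

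**Step 6: precision if all 14 are reported.** Hanley–McNeil at AUC 0.65, with Q1 = A/(2−A) = 0.4815 and Q2 = 2A²/(1+A) = 0.5121. For 15 and 55: variance = [0.2275 + 14 × (0.4815 − 0.4225) + 54 × (0.5121 − 0.4225)]/825 = 0.00714; half-width = 1.96 × 0.0845 = 0.17. With 7 events it is 0.23; with 21 it is 0.15.

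**The case against.** The strongest reply is that the protocol permits the biased route without prescribing it. Promise is undefined, much of the preceding analysis is across arms, and a choice on arm difference does no harm. The work is called exploratory throughout and no endpoint rests on these AUCs. A definition of promise, or internal validation, could sit in a statistical analysis plan that is not at hand.

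Much of this stands. It makes the point conditional and low in severity, and the absence of an optimism correction is not the finding. What remains is the rule itself, which makes observed promise sufficient on its own after steps that use outcome. An exploratory label does not lower an inflated AUC.

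Three stronger readings are tempting and are not supported:

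- That the planned sensitivity, specificity and predictive values are inflated by this filter. Section 9.2 applies them to the biomarkers as a whole, before the filter.
- That only the single best marker will be taken. The text does not say so; that scenario is the severe end of the illustration.
- That these AUCs will decide which cytokines go forward. Section 9.1 speaks of larger studies in general, just after a remark on sampling times, and mentions no shortlist.

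**Conclusion.** The point holds in conditional form. Where promise is judged on outcome in the same participants, the AUCs of the markers admitted that way are biased upward. With 15 events in 70, a true 0.65 shows about 0.72 under a p<0.05 rule (about 0.79 with 7 events and 0.71 with 21) and about 0.76 if the best of 14 is taken.

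These sizes rest on an assumed event count, an assumed correlation and an assumed meaning of promise. The direction of the bias held throughout the range tried, and its size shrinks as events increase. Markers admitted on plausibility fixed beforehand, or on arm difference alone, are not affected.

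This is a cheap improvement that the sponsor could make. It does not undermine the study.

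**What to change.** Replace the ROC entry rule in section 9.2 with wording such as:

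> For objective 2, the AUC with 95% CI will be reported for all 14 cytokines at the baseline sample, whatever the earlier results. Any further AUC or cut-off (other timepoints, change, grouped variables) for a marker chosen on its relation to outcome in these data will be labelled as data-selected and likely optimistic.

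Reporting all 14 removes the selection, and with it this bias. Baseline fits objective 2 because section 6.2 takes that sample "with the aim of characterising the inflammatory response to sepsis before, or at, the point of administration of the trial intervention". It is drawn at enrolment, which section 3 allows up to 12 hours after presentation, so it is the nearest available sample to presentation and not identical to it. Later timepoints and change scores stay open to exploration.

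A bootstrap optimism correction is optional. It must repeat the selection step in each resample, so it can be run only if an explicit selection rule is written first.

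Cost: two sentences and a little more analysis, with no new data. The sponsor should expect lower headline AUCs and wide intervals, about ±0.17 at an AUC of 0.65 with 15 events.
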